Clinical Trial Protocol: ADX-102-DED-013

Protocol Title: A Multi-Center, Phase 2, Randomized, Double-Masked, Parallel-Group, Vehicle-Controlled, Clinical Trial to Assess the Safety and Efficacy of Reproxalap Ophthalmic Solution (0.25% Novel Formulation) Compared to Vehicle in Subjects with Dry Eye Disease

Protocol Number: ADX-102-DED-013

Study Phase: 2

Investigational Product Name: Reproxalap Ophthalmic Solution (0.25% Novel Formulation)

IND/IDE/PMA Number: [REDACTED]

Indication: Dry Eye Disease

[figure not shown]
Investigators: Multi-center

Sponsor: Aldeyra Therapeutics, Inc.
[name]
[name]
Ora. Inc.
[name]
[name]

[figure not shown]
Contract Research Organization: [REDACTED]
[REDACTED]
[REDACTED]
[REDACTED]

[REDACTED]
08 March 2019

Amendment 1: 17 December 2019

MEDICAL MONITOR

SYNOPSIS

Protocol Title:	A Multi-Center, Phase 2, Randomized, Double-Masked, Parallel-Group, Vehicle-Controlled, Clinical Trial to Assess the Safety and Efficacy of Reproxalap Ophthalmic Solution (0.25% Novel Formulation) Compared to Vehicle in Subjects with Dry Eye Disease
Protocol Number:	ADX-102-DED-013
Investigational Product:	1) Reproxalap Ophthalmic Solution (0.25% Novel Formulation) 2) Vehicle Ophthalmic Solution (vehicle)
Study Phase:	2
Overall Study Design:	Multi-center, double-masked, parallel-group, vehicle-controlled, randomized clinical trial Prior to randomization , subjects will receive 14 consecutive days █ of vehicle, self-administered QID in both eyes, between Visits 1 and 2. Randomization will be 1:1 into one of two treatment arms (100 subjects per arm): 
1. Reproxalap administered QID for four weeks, followed by BID administration for eight weeks2. Vehicle administered QID for four weeks, followed by BID administration for eight weeks
Primary Objective:	Evaluation of the safety and efficacy of reproxalap compared to vehicle for the treatment of dry eye disease
Duration:	Approximately 14 weeks (98 days) including 12 weeks of treatment
Summary of Visit Schedule:	Nine visits over the course of approximately 14 weeks

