7.1.2 Primary Efficacy Endpoint

- The primary endpoint is the overall mean change from baseline in subject-reported ocular dryness score [REDACTED] assessed using MMRM from Week 2 to Week 12. The population used for analysis of ocular dryness score will be subjects who have a baseline ocular dryness score [REDACTED]

7.1.3

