9.3.2 Visit 1: Day -14 ± 2 – [REDACTED]

All subjects will undergo the following screening assessments:

[REDACTED]
[REDACTED] Consent/HIPAA

- Demographic Data and Medical/Medication/Ocular History
- Review of Inclusion/Exclusion Criteria
- Urine Pregnancy Test (for females of childbearing potential): Women of childbearing potential must have a negative urine pregnancy test to continue in the study
- Multi-symptom Visual Analogue Scale (VAS)
- [REDACTED]
- [REDACTED]
- [REDACTED]
- [REDACTED]
- BCVA Utilizing an ETDRS Chart
- Slit Lamp Biomicroscopy
- [REDACTED]
- Fluorescein Staining (corneal and conjunctival)
- Lissamine Green Staining (corneal and conjunctival)

[figure not shown]
[REDACTED]

- [REDACTED]
- [REDACTED]
- [REDACTED]
- Slit Lamp Biomicroscopy
- [REDACTED]
- IOP
- Dilated Fundoscopy
- Review of Inclusion/Exclusion Criteria
- Run-in Instillation at the Study Site: All subjects having a positive response (as defined above) and meeting all other screening eligibility criteria at the end of Visit 1 will receive run-in drops for dosing. Qualified subjects will self-administer their initial run-in dose bilaterally at the study site under the supervision of a trained technician.
- Run-in Dispensation: Prior to discharge from the study site on Day -14, subjects will be dispensed sufficient Run-in supply to last until Visit 2 and will be educated on self-administration of vehicle run-in. Subjects will be instructed to self-administer one drop QID in each eye until Visit 2. Subjects will be instructed NOT to instill run-in on the morning of their next scheduled study visit (Visit 2).
- AE Query
- Subjects will be scheduled for Visit 2.

[figure not shown]

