11.4 Statistical Analysis

11.4.1 General Considerations

Quantitative variables will be summarized descriptively using number of subjects (n), mean, standard deviation, median, minimum, and maximum. Qualitative variables will be summarized using counts and percentages.

All summaries will be presented by treatment group. Summaries will be provided for demographics, baseline medical history, concurrent therapies, and subject disposition.

For the purpose of summarization, medical history, concurrent therapies, and adverse events will be coded to MedDRA and WHO Drug dictionaries, as appropriate.

Baseline measures are defined as the last non-missing measure prior to the initiation of randomized study treatment at Day 1. Change from baseline will be calculated as follow-up visit value minus baseline value. Treatment comparisons between active and vehicle will be matched by dosing regimen and calculated as active minus vehicle.

All analyses will be 2-sided at a significance level of 0.05. 95% confidence intervals will be provided where appropriate.

The statistical analysis plan (SAP) will serve as the final determinant of the statistical procedures, notwithstanding anything herein.

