11.4.5 Primary Efficacy Analysis

The overall mean change from baseline in [REDACTED] from Week 2 to Week 12 will be analyzed using [REDACTED] in subjects in the ITTOD population.

The [REDACTED] will be fit with baseline value, treatment and visit, as well as the two-way interaction between treatment and visit. Change from baseline of the variable of interest (either ocular dryness or fluorescein nasal staining) will be the dependent variable.

An unstructured covariance structure will be used to model the within-patient correlation over time. The Kenward-Roger approximation will be used to estimate the denominator degrees of freedom. If the unstructured covariance structure matrix results in a lack of convergence under the default fitting algorithm used by PROC MIXED, the model will be fit using covariance matrices of the following order until convergence is met:

- Heterogeneous Toeplitz
- Heterogeneous First-order autoregressive
- Toeplitz
- First-order autoregressive

All the data from the two treatment groups will be included in the models. Comparisons between two treatment groups (for example, between reproxalap and vehicle) at a given visit or for combined visits will be obtained by comparing the corresponding least squares means via customized SAS statements in the model.

Change from baseline will also be analyzed using ANCOVA models with terms for baseline value and treatment group, two-sample t-tests, and Wilcoxon rank sum tests as sensitivity analyses.

[REDACTED]

[REDACTED]
[REDACTED]
[REDACTED]
[REDACTED]

[REDACTED]

- [REDACTED]
[REDACTED]
[REDACTED]
- [REDACTED]
[REDACTED]
[REDACTED]
[REDACTED]

Further details of the analysis plan will be described in statistical analysis plan document (SAP).

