2.1 Primary Measures

The primary efficacy measure for the trial are the following:

- [REDACTED] ocular dryness score measured by the Visual Analog Scale [REDACTED]
[REDACTED]
[REDACTED]
[REDACTED]

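### The readable primary model adjusts for only one of two scheduled pre-randomization dryness VAS scores; adding the Visit 1 score is a nearly free but uncertain gain in precision

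*Protocol*

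**What the plan says.** The primary endpoint (protocol 7.1.2) is the "overall mean change from baseline in subject-reported ocular dryness score" from Week 2 to Week 12. SAP 2.1 identifies the measure as the "ocular dryness score measured by the Visual Analog Scale".

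The multi-symptom VAS is listed at Visit 1 (protocol 9.3.2), ahead of the first run-in dose, and at Visit 2 (9.3.3), ahead of randomization. Section 9.3.1 asks for procedures to be done in the listed order. Between the two visits (Synopsis, Overall Study Design), "subjects will receive 14 consecutive days" of vehicle, "self-administered QID in both eyes, between Visits 1 and 2".

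Protocol 11.4.1 fixes one baseline: "Baseline measures are defined as the last non-missing measure prior to the initiation of randomized study treatment at Day 1". In 11.4.5 the primary model "will be fit with baseline value, treatment and visit, as well as the two-way interaction between treatment and visit". Of the sensitivity analyses, the same section says: "Change from baseline will also be analyzed using ANCOVA models with terms for baseline value and treatment group". Neither term list includes a Visit 1 score.

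Protocol 11.4.1 makes the SAP the final word on methods, and SAP section 1 says the same. The SAP's primary-model text (13.1 and 13.1.1) is redacted, as is part of 11.4.5.

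**The concern.** A single self-rated score combines the subject's usual level with that day's noise. A second score taken before randomization can help separate the two, and so can explain follow-up variation that Visit 2 alone leaves unexplained. The unstructured covariance in the MMRM does not recover this information, because it describes post-baseline changes only. In the readable model Visit 1 is neither an outcome nor a covariate.

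At stake is the width of the interval for the treatment difference. Because the added covariate is measured before randomization and the model is linear, it changes neither the estimand nor the validity of the test.

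**Working it through.** **The plan's own figure.** Protocol 11.3 gives 54 per arm for dryness at 90% power and alpha 0.05 (two-sided by 11.4.1). No effect or SD is readable, so 54 cannot be reproduced, only inverted: d = √(2/54) × (1.960 + 1.282) = 0.624. I treat 54 as the requirement for the model with Visit 2 alone, which is an assumption.

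**Inputs.** Weeks 2 to 12 cover Visits 4 to 9, that is, six follow-up scores. All correlations below are assumptions, with equal variances:
- ρ: among follow-up scores, and between Visit 2 and each of them
- r₁₂: between Visit 1 and Visit 2
- c: between Visit 1 and each follow-up score

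**Formulas.**
- Variance of the follow-up mean given Visit 2: V = (1 + 5ρ)/6 − ρ²
- Share of V removed by adding Visit 1: (c − ρ·r₁₂)² / [(1 − r₁₂²)·V]

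**ρ = 0.5, r₁₂ = 0.5.** V = 3.5/6 − 0.25 = 0.3333.
- c = 0.3: (0.30 − 0.25)² / (0.75 × 0.3333) = 0.0025/0.25 = 1%
- c = 0.4: (0.40 − 0.25)² / 0.25 = 0.0225/0.25 = 9%
- c = 0.5 (exchangeable): 0.0625/0.25 = 25%

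**Exchangeable, ρ = 0.7.** V = 4.5/6 − 0.49 = 0.26. The share is (0.70 − 0.49)² / (0.51 × 0.26) = 0.0441/0.1326 = 33.3%.

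**Zero gain.** The gain vanishes whenever c = ρ·r₁₂. One example is ρ = 0.5, r₁₂ = 0.6, c = 0.3. Under AR(1) it vanishes at every visit, because Visit 1 then says nothing beyond Visit 2.

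**Between the extremes.** A random intercept (share 0.3 or 0.5) plus a decaying part with correlation 0.5 per 14 days, solved by the same conditional-variance calculation, gives 3.5% or 7.4%.

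**Conversion to sample size and power**, with d held at 0.624:

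| Assumed structure | Variance reduction | n per arm for 90% | Power at 54 per arm |
|---|---|---|---|
| AR(1) | 0% | 54 | 90.0% |
| ρ = r₁₂ = 0.5, c = 0.3 | 1% | 54 | 90.3% |
| ρ = r₁₂ = 0.5, c = 0.4 | 9% | 50 | 92.5% |
| Exchangeable, 0.5 | 25% | 41 | 96.3% |
| Exchangeable, 0.7 | 33.3% | 37 | 97.8% |

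For example, at 9% the effective n is 54/0.91 = 59.3, and power is Φ(0.624 × √(59.3/2) − 1.96) = Φ(1.44) = 92.5%.

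**Sensitivity to r₁₂.** If Visit 1 is assumed to correlate no better with Visit 2, about two weeks later, than with follow-up (r₁₂ = c = 0.4, ρ = 0.5), the share is (0.40 − 0.20)² / (0.84 × 0.3333) = 14%. With r₁₂ = c = 0.3 it is 7%. These exceed the 9% and 1% above only because r₁₂ is lower.

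**Selection**, from 500,000 simulated subjects under the exchangeable structure. Keeping subjects above the mean at Visit 2 alone leaves the gain essentially unchanged (variance ratio 0.748 at ρ = 0.5). Keeping those above the mean at both visits gives a ratio of 0.855, so the gain falls from 25% to 14.5%. At ρ = 0.7 that ratio is 0.771, so the gain falls from 33.3% to 22.9%.

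**The case against.** The strongest reply is that nothing is wrong. The MMRM adjusts for baseline and keeps its type I error, and the run-in already serves a purpose by placing baseline after vehicle exposure and reconfirming eligibility at Visit 2. The governing SAP text is unseen and may already contain a Visit 1 term. The gain may also be nil: AR(1), under which it is zero, is on the protocol's own list of fallback covariance structures. Finally, 54 per arm is a floor. About 100 per arm are randomized, and if all of them qualified for the dryness population, power at d = 0.624 would already be about 99%.

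All of this limits the size and standing of the point. It does not remove it, because the data are already scheduled and the term costs almost nothing. AR(1) appears in 11.4.5 only as the last resort after non-convergence, not as a belief about the data.

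A reader might also infer that the Visit 2 dryness VAS is the entry gate and a stratifier as well as the baseline, and that Visit 1 is used for screening only. The readable text does not establish this. The first stratifier in 9.1.5 and inclusion criterion 13A are blacked out, and criterion 5 refers to a questionnaire that cannot be identified as the VAS. What is readable is that the baseline (Visit 2) dryness score defines the primary analysis population (7.1.2 and 7.1.8).

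**Conclusion.** The point holds as an optional, nearly free improvement. Two pre-randomization dryness scores are scheduled, and the readable primary and ANCOVA models use one.

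A reader might go further and conclude that the plan certainly throws precision away, or that a gain of about 14% (power from 90% to about 94%) can be expected. Neither is supported. The SAP model is redacted, and no correlation is given. The range runs from 0% to about 33% of the variance, and 1% to 9% follows from one plausible set of assumptions. Because the run-in separates the two scores, Visit 1 may predict follow-up less well than Visit 2 does. Any selection on the score at both visits would shrink the gain further. The power figures also require that 54 per arm was sized for the single-baseline model and that about that number qualify. If most of the 100 per arm qualify, the benefit is mainly a somewhat narrower interval.

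**What to change.** First confirm whether SAP 13.1.1 already includes a Visit 1 term. If it does not, then before unmasking:

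- Add the Visit 1 (pre-run-in, pre-CAE) dryness VAS score as a second fixed covariate in the primary model in protocol 11.4.5 and SAP 13.1.1.
- Add the Visit 1 nasal staining score to the staining models in the same way. No size has been worked out for that endpoint.
- Keep Visit 2 as the reference for change from baseline and for population membership.
- Fill a missing Visit 1 score with a treatment-blind value, for example the pooled mean, so that no subject drops out of the observed-data model. State also what happens if Visit 2 is missing: the last-value rule then makes Visit 1 the baseline, and the two covariates coincide for that subject.

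The Phase 2b trial cited in protocol 11.3, or blinded pooled data from this trial, could show whether the gain is worth having. The cost is about one degree of freedom and a line of SAP text and program code, with no new data or visits.

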6 STUDY POPULATION

6.1 Number of Subjects (approximate)

It is estimated that approximately 500 subjects will be screened to enroll approximately 200 randomized subjects (100 in each group). Subjects will be randomized in a 1:1 ratio of Reproxalap Ophthalmic Solution (0.25% Novel Formulation) to Vehicle Ophthalmic Solution.

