11.3 Sample Size

Based on the results of a Phase 2b clinical trial of reproxalap in dry eye disease subjects (ADX-102-DED-009), for the outcome measurements of ocular dryness VAS score and nasal fluorescein staining, approximately 100 subjects per randomized arm will be evaluated in ADX-102-DED-013. Sample size estimates were made assuming an alpha of 0.05 and power of 90% for the two efficacy populations, one with baseline staining severity of 2 units or more and the other with dryness score severity of 3 units or more. Using PASS (software version 14, NCSS, LLC), the sample size estimated for staining was 39 per treatment arm (78 total); the sample size estimated for dryness score was 54 per treatment arm (108 total).

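### If both the unstructured and the heterogeneous Toeplitz fits fail, the primary MMRM can end on an autoregressive covariance with no robust standard error visible, which can understate the standard error of the Week 2-12 mean

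*Protocol*

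**What the plan says.** Protocol 11.4.5 models change from baseline with baseline value, treatment, visit and treatment-by-visit, under an unstructured within-subject covariance. "The Kenward-Roger approximation will be used to estimate the denominator degrees of freedom".

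If the unstructured fit does not converge with PROC MIXED's default algorithm, "the model will be fit using covariance matrices of the following order until convergence is met". The order is heterogeneous Toeplitz, then "Heterogeneous First-order autoregressive", then Toeplitz, then first-order autoregressive. Fitting stops at the first structure that converges. Section 11.4.5 applies this model to ocular dryness and to nasal fluorescein staining, each as its own dependent variable.

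The primary endpoint (7.1.2) is the overall mean change from Week 2 to Week 12. By the visit schedule that covers Visits 4 to 9: Weeks 2, 4, 6, 8, 10 and 12. On the test level, 11.4.1 says "All analyses will be 2-sided at a significance level of 0.05".

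The visible text mentions no empirical (sandwich) standard error and no second attempt at the unstructured matrix. The SAP takes precedence over the protocol on methods (protocol 11.4.1; SAP section 1), and its text on the dryness analysis (13.1.1) is redacted.

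**The concern.** The primary contrast averages six visits, so its variance depends on every pairwise correlation, including those between visits far apart. A first-order autoregressive structure makes correlation fall geometrically with lag. If some subjects are persistently drier than others, the true long-lag correlations stay high, the fitted ones are too low, and the standard error of the average comes out too small.

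Kenward-Roger allows for the covariance parameters having been estimated. It does not correct for having chosen the wrong structure. An autoregressive fit with model-based standard errors can therefore give an anti-conservative primary p-value and a confidence interval that is too narrow. The primary test comes first in the sequential procedure of 11.4.4, so a false rejection there would also open the next gate.

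**Working it through.** **Inputs from the documents.** Two-sided alpha 0.05 (11.4.1); 54 subjects per arm for the dryness population (11.3); 1:1 allocation (6.1); six visits in the primary average (7.1.2 and the visit schedule). The visible text gives no within-subject correlation, SD, effect size or dropout rate, so every correlation below is an assumption. So is complete data.

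**The plan's own figure.** "Sample size estimates were made assuming an alpha of 0.05 and power of 90% for the two efficacy populations", but no effect size or SD is visible, so 54 per arm cannot be reproduced. It can only be inverted: d = √(2(1.960 + 1.282)²/54) = 0.624. Nothing below depends on this value.

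**When an autoregressive form is reached.** Heterogeneous AR(1) needs two failures (unstructured, heterogeneous Toeplitz). AR(1) needs four. Covariance parameters for six visits, in the order tried: 21, 11, 7, 6, 2.

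**Formulas.** With unit variance and T equally weighted visits, the variance of a subject's mean is

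- compound symmetry: [1 + (T − 1)ρ]/T
- AR(1): [T + 2 Σ (T − k)ρᵏ]/T², summed over k = 1 to T − 1

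When the truth is compound symmetry with correlation ρ, the best-fitting AR(1) (smallest Kullback-Leibler distance) has lag-one correlation ρ, and heterogeneous AR(1) gives the same fit. The SE ratio is the square root of fitted over true variance. Type I error is 2·P(t₁₀₆ > 1.983 × ratio).

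**Worked case, T = 6, ρ = 0.4.** The sum is 5(0.4) + 4(0.16) + 3(0.064) + 2(0.0256) + 0.01024 = 2.8934. The AR(1) variance is (6 + 5.7869)/36 = 0.3274. The true variance is (1 + 2.0)/6 = 0.5000. The ratio is √(0.3274/0.5000) = 0.809, and type I error is 11.2%.

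| Assumed ρ (compound symmetry) | SE ratio | Type I error |
|---|---|---|
| 0.4 | 0.809 | 11.2% |
| 0.5 | 0.818 | 10.8% |
| 0.6 | 0.838 | 10.0% |
| 0.7 | 0.867 | 8.9% |
| 0.8 | 0.903 | 7.6% |

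**Other assumed truths, autoregressive fit.**

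- Random intercept (variance share 0.2-0.6) plus AR(1) residual: 7.3-8.0% with residual correlation 0.3, 6.1-6.5% with 0.5, 5.4-5.5% with 0.7 (normal reference).
- Compound symmetry with rising SD, random slope, and decay to a plateau: 7.6-10.7%.
- AR(1) true: 5.0%.

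**Toeplitz fits.** Toeplitz gives 5.0% under compound symmetry. Under the rising-SD, random-slope and plateau truths, Toeplitz and heterogeneous Toeplitz give 4.8-5.0%.

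**Simulation check.** 4,000 trials per setting with REML estimation, and a t reference with 2n − 2 df standing in for Kenward-Roger. Under compound symmetry with ρ = 0.3, 0.5, 0.7 and 0.9, AR(1) rejected in 10.3, 11.8, 9.2 and 6.3% of trials at 54 per arm, and in 10.6, 10.9, 8.5 and 6.2% at 100 per arm. The unstructured fit gave 4.7-5.5%. More subjects do not cure the problem.

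**With the fix.** In balanced complete data the sandwich SE is small by a factor √(53/54) = 0.991, which gives 5.2%.

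**The case against.** The strongest objection is that the rule rarely gets this far. The first fallback is heterogeneous Toeplitz, which is sound. With 21 covariance parameters and 54 to 100 subjects per arm, the unstructured fit should normally converge. A reader might infer that any use of the fallback list inflates the error, or that 6-11% is the trial's type I error. The documents support neither. If the chance of ending on an autoregressive form were 1% (an assumption), overall error even at the worst correlation would be 0.99 × 5 + 0.01 × 11.2 = 5.06%; at 5% it would be 0.95 × 5 + 0.05 × 11.2 = 5.31%. This part of the objection stands.

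A reader might also infer that every later test inherits the error. It does not. The staining models are fitted separately and converge or fail on their own; a false primary rejection only opens the gate. The order of tests is redacted.

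Three further points stand in part:

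- The SAP governs, and its redacted text may already provide a robust standard error or a refit. The absence can be asserted only for the visible text.
- Non-convergence would more plausibly come with sparse or near-singular data, which the complete-data calculation does not represent.
- The listed order steps down in parameter count and keeps visit-specific variances for as long as it can, so placing heterogeneous AR(1) before Toeplitz is defensible.

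The ANCOVA, t-test and Wilcoxon sensitivity analyses could expose a discordant result, but they do not replace the primary p-value. A fallback rule exists for the unlikely case and should be valid when it is used.

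**Conclusion.** The concern holds in a limited form. If the unstructured and heterogeneous Toeplitz fits both fail, the visible rule permits an autoregressive fit with no robust standard error. Given such a fit, the standard error of the Week 2-12 mean is 0.81 to 0.90 of its true value under compound symmetry with correlation 0.4-0.8, and type I error is about 8-11%. It is about 5.4-8% under a random intercept plus autoregressive residual, and there is no inflation if AR(1) is true.

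These figures assume complete data, equal visit weights, a t reference instead of an exact Kenward-Roger calculation, and correlations that the documents do not give. Neither document gives a probability for the double failure. The weakness is in a contingency rule and is not an expected error in the primary result. Priority is low to moderate.

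**What to change.** In protocol 11.4.5, and in the SAP unless its redacted text already covers this:

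1. Before leaving the unstructured matrix, refit it with other starting values or a Cholesky or factor-analytic parameterisation.
2. For any structured fallback, use the empirical (sandwich) standard error with a stated degrees-of-freedom rule such as between-within. Keep Kenward-Roger for the unstructured fit.

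Optionally, drop the autoregressive steps or place Toeplitz ahead of them.

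The cost is a few lines of text and one SAS option. There are downsides: Kenward-Roger is not available with the sandwich standard error, which is about 1% small at 54 per arm. The sandwich also does not remove bias in the treatment estimate when the covariance is misspecified and subjects drop out. That is a further reason to try harder for the unstructured fit first.
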